9.5. Patient-Reported Outcomes and Symptom Questionnaires

Descriptive statistics of observed, change from baseline and percentage change from baseline values will be provided at scheduled visits during double-blind treatment phase and open-label extension phase, respectively. Descriptive statistics of baseline of active treatment, change and percentage change from baseline of active treatment values at visits in open-label extension phase will be provided additionally. The change from baseline and percentage change from baseline values to each visit will be analyzed using similar statistical methodology for all patient-reported outcomes and symptom questionnaires unless specified otherwise at visits during double-blind treatment phase.

The patient-reported outcomes and symptom questionnaires will include the following:

- Total score of Steroid Toxicity Questionnaire where lower scores indicate better status.
- Scores of each of the 5 King's Sarcoidosis Questionnaire Modules (General Health Status, Lung, Medication, Skin, and Eyes) where higher scores indicate improvement.
- Total scores of each of the 4 King's Sarcoidosis Questionnaire overall scales (Lung Health Status [General Health Status module and Lung module], Skin Health Status [General Health Status module and Skin module], Eye Health Status [General Health Status module and Eye module], Lung-Skin Health Status [General Health Status module, Lung module and Skin module]) where higher scores indicate improvement and a change of 4 points is considered clinically meaningful.
- Total score of Fatigue Assessment Scale where lower scores indicate improvement and a change of 4 points is considered clinically meaningful.
- Patient's Global Assessment where higher scores indicate better status.
- Physician Global Assessment where higher scores indicate better status.
- Medical Research Council Dyspnea Scale where lower scores indicate better status.
- Total score and each score of the 3 domains (Physical, Psychological and Social) of Leicester Cough Questionnaire where higher scores indicate better health status.
- Work Productivity and Activity Impairment (WPAI)

Calculation for above scores are provided in Appendix 15.2.

The treatment difference between Acthar and placebo for both change from baseline and percentage change from baseline to visits in the double-blind treatment phase in each outcome or questionnaire score will be evaluated using a two-sample T-test. Wilcoxon rank sum test may be used if the data are not normally distributed. Percentage change in King's Sarcoidosis Questionnaire and Fatigue Assessment Scale will be plotted in line graph over time showing the means and SEs. For WPAI data, only a listing will be provided.

If result is missing at a post-baseline visit, the missing result will be imputed using the LOCF method. No imputation will be applied to the open-label extension phase. All

summaries and analyses will be conducted on both the observed values and the LOCF values.

Listings will be provided for each patient-reported outcome and symptom questionnaire by subject and visit.

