8. STUDY DESIGN

8.1. Description

This is a multicenter, randomized, double-blind, placebo-controlled exploratory study evaluating the efficacy and safety of Acthar Gel in the treatment of pulmonary sarcoidosis.

The study will have 3 phases: Screening (up to 28 days); double blind treatment (24 weeks); and an optional open-label, 24 weeks extension. A follow-up visit will be conducted 4 weeks (\pm 2 days) after the last dose of IMP is administered.

Following signature of the ICF and a screening period of up to 28 days, subjects who meet all eligibility criteria will be randomly assigned to receive either 1 mL (80 U) of Acthar Gel or 1 mL of a matching placebo SC 2 \times /week. Subjects will be assigned to treatment in a 1:1 ratio with up to 50 subjects per arm for a total of approximately 100 subjects.

Dose reduction of 50% may be implemented once during the study, if a subject meets one of the following prespecified safety criteria based on clinical judgment:

- Uncontrolled hypertension (newly developed or worsening of existing hypertension) before/or in conjunction with addition/adjustment of antihypertensive therapy.
- Uncontrolled diabetic signs/symptoms (newly developed or worsening of existing diabetes) before/or in conjunction with addition/adjustment of antihyperglycemic therapy.
- Unacceptable toxicity defined as any AE of at least moderate intensity not adequately controlled by concomitant medication use or other non IMP-related measure

The justification for dose reduction will be captured in the eCRF. Subjects will remain on the 40 U or matching placebo 2 \times /week for the remainder of the study. Subjects who, despite dose reduction, continue to experience any of the above mentioned AEs, (meet a criteria as above) or experience another event will be withdrawn from the study due to AE ([Section 12.3](#)).

Subjects will be followed every 4 weeks (\pm 5 days) for 24 weeks (Visit 2 to Visit 8). During each visit following Visit 2, steroid tapering evaluation will occur based on the corticosteroid tapering algorithm ([Section 7.2.4](#)). A justification for any deviation will be captured in the eCRF.

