3.2. Study Endpoints

3.2.1. Efficacy Endpoints

The endpoints for the efficacy objective are:

- Sarcoidosis treatment score (STS) response rate at 24 weeks (Visit 8).
- STS response rate at 48 weeks (Visit 11).
- Physician and subject independent responses to the question “Would you choose to continue current treatment?” at 24 and 48 weeks.
- Time to response (TTR) as evaluated at earlier time points (Weeks 4 to 20) as determined by the investigator based on clinical judgment and the following parameters:
 - Patient reported outcomes.
 - Corticosteroid tapering.
 - Patient Global Assessment.
 - Physician Global Assessment

- Pulmonary function test (PFT) at applicable time points.
- Extrapulmonary response by extrapulmonary Physician Organ Severity Tool (ePOST).
- Supportive efficacy endpoints per applicable time points.
 - Six-minute walk test (6MWT).
 - Symptom relief (Leicester Cough Questionnaire, Medical Research Council Dyspnea Scale, steroid toxicity questionnaire).
 - Chest x-ray (CXR) (including Scadding score).
- Percentage change in overall diffusion capacity of the lung for carbon monoxide (DLCO).
- Percentage of subjects with improvement in DLCO of $\geq 5\%$; $\geq 10\%$; and $\geq 15\%$.
- Percentage change in overall forced vital capacity (FVC).
- Percentage of subjects with improvement in FVC of $\geq 5\%$, $\geq 10\%$, and $\geq 15\%$.
- Percentage of subjects with improved/stable/deteriorate side-by-side comparison of high-resolution computed tomography (HRCT) on a 5-point Likert score: much worse; worse; unchanged; better; much better (central reader).
- Percentage of subjects with improved/stable/deteriorated side-by-side comparison of CXRs on a 5-point Likert score: much worse; worse; unchanged; better; much better (central reader).
- Percentage change in Scadding score (side-by-side comparison of CXRs by a central reader).
- Percentage change in patient-reported outcomes and symptom questionnaires.
- Percentage failed corticosteroid taper.
- Time to failed corticosteroid taper (for subjects failing taper).
- Change from baseline in Work Productivity and Activity Impairment (WPAI) over time

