4.1. Sample Size

Formal sample size calculations were not performed. The sample size is based on recent literature of comparative studies ([Gibson et al., 1996](#); [Baughman et al., 2006](#); [Judson, 2014](#)) in sarcoidosis. There are 55 subjects randomized to this study.

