4.2. Randomization, Stratification, and Blinding

An interactive telephone/web response system will be used to allocate eligible subjects to each treatment group. Subjects will be randomized according to computer-generated allocation scheme to receive either Acthar Gel 1 mL (80 U) or placebo 1 mL administered twice a week in a 1:1 ratio. Both investigators and the subjects will be blinded to the treatment assignment. A block randomization will be performed.

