- Two baselines, baseline of overall study and baseline of active treatment, have been defined. Baseline of overall study is defined as the last assessment prior to the first dose of IMP at the double-blind treatment phase. Baseline of active treatment is defined as the last assessment prior to the first dose of active treatment in either the double-blind treatment phase or the open-label extension phase. All the analysis in the open-label extension phase that involves presenting change and/or percent change from baseline will present change/percent change from both baselines.
- Summary statistics will be provided for all study variables with descriptive statistics (number of subjects, mean, standard deviation (SD), median, minimum,

and maximum) for numerical (or continuous) variables. Frequency and percentages will be calculated for categorical variables.

- Unless specified otherwise for a given analysis, all statistical tests, when applicable, will be 2-sided with a significance level of 0.05.
- All data collected will be presented in listings, sorted by treatment group, subject identifier and date/time of procedure or event, if applicable.

All analyses will be conducted using SAS® Version 9.4 or higher. The Medical Dictionary for Regulatory Activities (MedDRA) version 23.0 will be used for coding adverse events (AEs), and medical and surgical histories. Prior or concomitant medication data will be coded according to the Anatomical Therapeutic Chemical (ATC) coding scheme of the World Health Organization (WHO) Drug Dictionary (Enhanced B2 dated March 2018 version, or higher) level 2 term.

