9.4.2. Scadding Score

The number and percentage of subjects for each Scadding score (Stage 0, Stage I; Stage II; Stage III; and Stage IV) will be summarized at week 24 (Visit 8) and week 48 (Visit 11) by treatment group. Pearson's chi-square test (or Fisher's exact test if any expected count is less than 5) will be used to compare the treatment difference between treatment groups.

The Scadding score will be converted to numeric score in the following manner:

0 - Stage 0

1 - Stage I

2 - Stage II

3 - Stage III

4 - Stage IV

Descriptive statistics of observed, change from baseline and percentage change from baseline values will be presented by treatment group at week 24 (Visit 8) and week 48 (Visit 11) for the Scadding score. Baseline of active treatment, change from baseline and percentage change from baseline values will be presented as well for week 48 (Visit 11). Note that the percentage change will not be calculated for subjects with Scadding score stage 0 at baseline.

The treatment difference between Acthar and placebo for both change from baseline and percentage change from baseline to week 24 (Visit 8) in Scadding score will be evaluated using a Wilcoxon rank sum test.

A listing will be provided for the imaging data and Scadding score by subject and visit.

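### SAP 9.5 puts unadjusted t-tests on percentage change in questionnaire scores, with no zero-baseline rule, although absolute change (already tested) is the sounder quantity and could be baseline-adjusted

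*SAP*

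**What the plan says.** Both documents name the endpoint as a percentage; in SAP 3.2.1 it reads "Percentage change in patient-reported outcomes and symptom questionnaires". Section 9.5 then plans treatment comparisons of two quantities at each double-blind visit. One is the absolute change. For the other, "percentage change from baseline to visits in the double-blind treatment phase in each outcome or questionnaire score will be evaluated using a two-sample T-test". Neither test adjusts for baseline. A Wilcoxon rank sum test is allowed where data are not normal, but it is optional and no criterion for switching is given. Everything is run on observed and on LOCF data. WPAI is only listed.

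Section 9.5 does not say what happens when the baseline is zero. Section 9.4.2 does, for the Scadding score: "the percentage change will not be calculated for subjects with Scadding score stage 0 at baseline". Scadding change and percentage change are both compared there by Wilcoxon.

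The setting is small and carries no power claim. SAP 4.1 says "Formal sample size calculations were not performed" and "There are 55 subjects randomized to this study", against a protocol target of about 100. By Section 4.3, "all statistical tests, when applicable, will be 2-sided with a significance level of 0.05".

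**The concern.** Percentage change divides by the baseline, which causes four problems here.

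- **Undefined values.** A subject with a zero baseline has no percentage change. Section 9.5 leaves open whether that subject is dropped, set to a value or handled otherwise.
- **Small denominators.** A low but non-zero baseline turns a modest change into a very large percentage. A few such values inflate the variance on which a t-test depends.
- **Ordinal grades.** MRC dyspnea is a single grade from 1 to 5. A ratio of two grades has no clear meaning.
- **Conflict with the plan's own yardstick.** Protocol 7.2.6 and 7.2.7 and SAP 9.5 treat an absolute change of 4 points as meaningful for KSQ and the Fatigue Assessment Scale (FAS), and the STS scores both in absolute points. A fixed absolute change is a different percentage at each baseline.

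At stake is the reading of the questionnaire results. Each score gets two p-values per visit that can point different ways. The line graphs planned in 9.5, for KSQ and FAS, show the percentage version.

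**Working it through.** **1. Which scores can be zero at baseline**

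- Steroid Toxicity total: 11 items scored 0 to 4 (SAP 15.2.1), so 0 to 11 × 4 = 44. Zero is possible and is the best score.
- KSQ modules and combined scales: every conversion table in SAP 15.2.2 starts at 0.0. Zero is possible but is the worst score, so it should be rare.
- FAS: 10 items scored 1 to 5 (Protocol Attachment 5), so 10 to 50. Zero is impossible.
- MRC: grades 1 to 5 (Attachment 8). Zero is impossible.
- Leicester Cough (LCQ) domains: means of items scored 1 to 7 (SAP 15.2.7, Attachment 9). Zero is impossible.
- Patient and physician global assessments: the end points are in figures not shown. A zero minimum is an assumption.

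**2. What the percentage does to equal steps**

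- FAS, 4 points: 4/20 = 20% from a baseline of 20, and 4/40 = 10% from 40.
- KSQ General Health, one raw point (SAP 15.2.2): (15.7 − 9.3)/9.3 = 69% near the bottom, and (100.0 − 91.0)/91.0 = 10% at the top.
- MRC, one grade worse: 1 to 2 is +100%, and 4 to 5 is +25%.

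**3. Power**

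The plan has no power figure to reproduce. The documents supply the two-sided 0.05 level, 1:1 allocation ("administered twice a week in a 1:1 ratio") and 55 randomized. Arm sizes are not stated, so 28 v 27 is taken. Means, SDs, effects and correlations are assumptions.

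With baseline B and follow-up F, the simulation compared a t-test on F − B, a t-test on 100 × (F − B)/B with B = 0 dropped, and ANCOVA of F − B on treatment and B. Scores were clipped to their ranges. There were 40 scenarios of 500 replicates (Monte Carlo SE about 2 points), with correlation 0.5 or 0.7 and additive or proportional effects.

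| Scale (assumed mean, SD, effect) | % change, t | Change, t | ANCOVA | Power ratio, % to change | Zero baseline |
|---|---|---|---|---|---|
| FAS (25–30, 8, −5) | 0.56–0.83 | 0.58–0.88 | 0.74–0.95 | 0.88–0.98 | 0% |
| MRC (2.5, 1, −0.6) | 0.46–0.61 | 0.47–0.74 | 0.63–0.88 | 0.82–0.98 | 0% |
| LCQ domain (5, 1.2, 0.8) | 0.46–0.70 | 0.59–0.81 | 0.68–0.89 | 0.78–0.87 | 0% |
| Steroid Toxicity (8–15, 6–8, −4 to −5) | 0.38–0.71 | 0.56–0.93 | 0.73–1.00 | 0.53–0.85 | 0.1–3.6% |
| KSQ General Health (55, 18, 10) | 0.27–0.53 | 0.47–0.73 | 0.52–0.76 | 0.58–0.72 | 0.1–0.2% |
| Global scale, if 0–10 (3–5, 2–2.2, 1.3) | 0.23–0.63 | 0.48–0.85 | 0.57–0.88 | 0.48–0.74 | 2–11% |

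Under the t-test, percentage change was weaker than absolute change in every scenario. With Wilcoxon on both quantities the ratio was 0.68 to 1.16, so ranking recovers much of the loss. ANCOVA gained 0 to 21 points over the absolute-change t-test, mostly 3 to 13. The extremes were 0.76 to 0.76 (global scale) and 0.72 to 0.93 (Steroid Toxicity).

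**4. A low, skewed Steroid Toxicity score**

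Assumed: true score gamma (shape 1.8, scale 5, mean 1.8 × 5 = 9), measurement noise SD 3, rounded and clipped to 0–44, 3,000 replicates.

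| Effect | % change, t | Change, t | ANCOVA |
|---|---|---|---|
| Fall of 3.5 points | 62% | 79% | 83% |
| Rise of 3.5 points | 44% | 85% | 88% |
| Proportional, similar mean size | 41% | 81% | 91% |

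A rise is plausible, since Protocol 6.4 says the common adverse reactions resemble those of corticosteroids. About 4.4 of 55 subjects (8%) had a zero baseline. The two t-tests fell on opposite sides of 0.05 in 26% of replicates for the fall and 44% for the rise.

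**The case against.** The case for leaving the plan alone has real content.

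- **Absolute change is already tested.** A reader who sees only the percentage endpoint might infer that the efficient analysis is missing. It is not: 9.5 tests both quantities at every double-blind visit. What the plan lacks is baseline adjustment and a statement of which result counts.
- **Wilcoxon is available.** It deals with most of the outlier problem. It does not define a value at zero, and without a criterion the choice of test stays open until data are seen.
- **Scadding is handled better.** A reader might infer that Scadding stages are t-tested and that stage 0 subjects leave the analysis. Section 9.4.2 uses Wilcoxon, and those subjects drop out of percentage change only. They stay in the stage-change test and the stage table.
- **Few subjects are lost.** Zero is impossible on three of the instruments and rare on KSQ General Health. The 8% above belongs to one assumed low, skewed score.
- **The protocol names percentage change.** Testing it is faithful to the protocol, and the study is exploratory. That explains the test but does not make the quantity a good one.

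**Conclusion.** The point stands as a limited one. Section 9.5 puts unadjusted t-tests on a quantity that is undefined for some possible baselines, has no clear meaning for MRC, and disagrees with the plan's own 4-point standard. It gives neither a zero-baseline rule nor a criterion for switching to Wilcoxon.

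The size depends on the scale. The power of the percentage-change t-test relative to absolute change ranged from 0.98 (2% lower) to 0.48 (about half). A reader might infer that power is halved in general. That is not supported: halving appears only for an assumed 0–10 global scale and some Steroid Toxicity settings, with KSQ General Health losing 28% to 42%, while FAS loses 2% to 12%. Nor does the plan as a whole lose that power, because the absolute-change test is printed beside it.

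All means, SDs, effects, correlations and arm sizes are assumptions. The STS response rate is untouched, because KSQ and FAS enter it through absolute changes.

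**What to change.** - In 9.5, make baseline-adjusted absolute change the tested quantity for questionnaire scores, by ANCOVA at each visit or by the MMRM whose code in SAP 15.4 already has a baseline term (the model text in 9.3 does not list one).
- For MRC, use a rank or ordinal method.
- Keep percentage change as a descriptive summary, and state what is done when the baseline is zero.
- For Scadding, keep the planned Wilcoxon on stage change and drop only the percentage-change test.
- Record the change in SAP Section 13.

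The plan has a precedent: the DLCO and FVC endpoints are named as percentage change, yet 9.3 tests change in % predicted.

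The cost is SAP wording and some reprogramming, with no new data. It also removes tests. Section 9.5 lists 18 tested scores (1 Steroid Toxicity, 9 KSQ, 1 FAS, 2 global assessments, 1 MRC, 4 LCQ). Over six post-baseline double-blind visits and two data versions, that is 18 × 6 × 2 = 216 percentage-change p-values. The downside is that the protocol's named quantity no longer has a p-value, which Section 13 should say openly.

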The first study was a retrospective chart review of 47 patients with advanced sarcoidosis seen at 2 clinical centers who received at least 1 dose of Acthar Gel with at least 6 months of posttreatment follow-up. All patients initially received Acthar Gel 80 U intramuscular or SC administration twice a week (2×/week). Eighteen patients (37%) discontinued drug within 6 months due to study participation cost (4 patients), death (2 patients), or drug toxicity (11 patients), or noncompliance (1 patient). Of the remaining 29 patients, 11 experienced objective improvement in 1 or more affected organs. All but 2 patients noted disease improvement or oral glucocorticoid reduction. Twenty-one patients were treated for more than 6 months (median 274 days). Nineteen patients were taking prednisone at time of starting Acthar Gel: 17 had their prednisone dosage reduced by more than 50%, and 1 patient discontinued cyclophosphamide therapy. Acthar Gel treatment for at least 3 months was associated with objective improvement in a third of the patients. A third of the patients were unable to take treatment for at least 3 months ([Baughman et al., 2016](#)).

The second study was a prospective study of 16 patients with chronic pulmonary sarcoidosis receiving prednisone therapy with deterioration by at least 5% in FVC in the previous year. Acthar Gel was administered at a loading dose of 80 U SC for 10 days. Patients were randomized at Day 14 to receive either 40 U or 80 U Acthar Gel 2×/week for 24 weeks. The dose of prednisone was modified by the clinician who was blinded to the patient's dosage of Acthar Gel. At Week 24, there was a decrease in the dose of prednisone and improvements in DLCO, the King's Sarcoidosis Questionnaire (general health status), and the Fatigue Scale. There was no significant change in FVC % predicted. For the positron emission tomography scan, there was a significant fall in the standard uptake value of the lung lesions. Only 3/8 patients remained on 80 U repository corticotropin for full 24 weeks. There was no significant difference in the response to therapy for those treated with 40 U vs 80 U Acthar Gel. The authors concluded that Acthar Gel treatment was prednisone-sparing and associated with significant improvement in DLCO, positron emission tomography scan, and patient-reported outcome measures. A dose of 40 U repository corticotropin 2×/week was as effective as 80 U Acthar Gel and was better tolerated ([Baughman et al., 2017](#)).

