11.3. Visits 3, 4, 6, and 7, Procedures

The investigator or designee will complete the following procedures at Visit 3, 4, 6, and 7:

- Patient reported outcomes. Patient-reported outcomes include: Steroid toxicity questionnaire; King's Sarcoidosis Questionnaire ([Attachment 4](#)); Fatigue Assessment Scale ([Attachment 5](#)); Patient's Global Assessment ([Attachment 6](#)); Medical Research Council Dyspnea Scale ([Attachment 8](#)); Leicester Cough Questionnaire ([Attachment 9](#)), WPAI ([Attachment 10](#)).
- Vital sign determinations. Vital signs will be obtained after the subject has been seated for 5 minutes (minimum) and will include systolic and diastolic blood pressures, pulse rate, and respiratory rate (see [Section 14.4](#)).
- Weight determination. Every effort should be made for weight to be measured by the same calibrated scale at every visit.
- Physical examination (see [Section 14.3](#)). Full physical examination will include targeted examination per organ involved. All efforts must be undertaken for the same physician to perform the physical examination per subject, per organ involved at each visit.
- ePOST: All efforts must be undertaken for the same physician to perform the ePOST ([Attachment 3](#)) side-by-side with prior evaluations.
- Physician Global Assessment ([Attachment 7](#)).
- Clinical laboratory tests:
 - Complete blood count.
 - Clinical chemistry, including liver function tests. Samples will be collected from subjects who have been fasted for at least 12 hours.
 - HbA1C.
 - Human chorionic hormone (urine pregnancy testing, females of child bearing potential only – local laboratory).

- Subject diary review.
- Study drug accountability.
- Corticosteroid tapering. (At Visit 3, if the subject improved or was stable at both Visit 2 and Visit 3, tapering can be applied).
- AEs and concomitant medications.
- Contact IXRS and dispense IMP kits and encourage compliance.
- Remind the subjects to arrive in fasting condition (drinking water is permitted) for Visits 4, 5, 6, and 7 and to bring all IMP kits including used and unused vials to each visit in a cooler.

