11.4. Visit 5 Procedures

In addition to all procedures described in [Section 11.3](#) the following will also be performed at Visit 5 by the investigator or designee:

- C-reactive protein.
- 25-Hydroxy vitamin D, 1, 25-dihydroxy vitamin D, parathyroid hormone (Visit 5 only).
- Urinary analysis (local laboratory).
- Subject diary review.
- Study drug accountability.
- Biomarkers sample collection (including RNA, if genetic ICF signed).
- PFT.

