9.3. Pulmonary Function Tests

Descriptive statistics of observed and change from baseline will be presented for PFT results including DLCO % predicted and FVC % predicted at each scheduled visit during double-blind treatment phase and open-label extension phase, respectively. In addition, change from baseline of active treatment will be presented for open-label extension phase.

The treatment difference between Acthar and placebo for change from baseline to each visit in the double-blind treatment phase in DLCO % predicted and FVC % predicted will be evaluated using a two-sample T-test. Change in DLCO % predicted and FVC % predicted will be plotted in line graph over time showing the means and SEs by visit across both study phases.

Also, the treatment effect for the change from baseline to each scheduled visit in the double-blind treatment phase in DLCO % predicted and FVC % predicted will be estimated using a mixed effect model with repeated measures (MMRM) model. The MMRM model will use change from baseline as the response variable, and include visit, treatment group, and visit-by-treatment group interaction as covariates. Additionally, visit (categorical) will be specified as a repeated effect and unstructured (UN) correlation matrix will be used to model intra-subject correlation. In case a convergence issue will arise using the UN correlation matrix, (1) first-order autoregressive (AR1) or (2) Compound Symmetry (CS) will be used to enable model convergence (in this order). The least square (LS) mean difference with 95% CI and p-value will be presented.

In addition, improvement in DLCO % predicted and FVC % predicted will be explored by using criteria ($\geq 5\%$, $\geq 10\%$ and $\geq 15\%$, respectively). Number and percentage of subjects with improvement will be provided at each scheduled visit by double-blind treatment phase and open-label extension phase. Pearson's chi-square test (or Fisher's exact test if any expected count is less than 5) will be used to compare the treatment difference between treatment groups in the double-blind treatment phase. The following endpoints will be included:

- Percentage of subjects with improvement in DLCO % predicted of $\geq 5\%$
- Percentage of subjects with improvement in DLCO % predicted of $\geq 10\%$
- Percentage of subjects with improvement in DLCO % predicted of $\geq 15\%$
- Percentage of subjects with improvement in FVC % predicted of $\geq 5\%$

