15.4. SAS Procedures

- T test

```
ods output ttests=ttest;
proc ttest data=xxx sides=2 alpha=0.05 h0=0;
  class TRT;
  var AnalVar;
run;
```

- Pearson's chi-square test

```
proc freq data=xxx;
  tables TRT*AnalVar /chisq;
  output out=chisq pchi;
run;
```

- Fisher's exact test

```
proc freq data=xxx;
  tables TRT*AnalVar / fisher;
  output out= fisher exact;
run;
```

- MMRM

```
ods output lsmeans=lsm diffs=diff;
proc mixed data=xxx;
  class TRT AVISITN USUBJID;
  model AnalVar = BASVAR TRT AVISITN TRT*AVISITN;
  repeated AVISITN / type=UN subject=USUBJID;
  lsmeans TRT*AVISITN / diff cl;
run;
```

Statistical Analysis Plan (SAP) Client Approval Form

Client:	Mallinckrodt ARD, LLC
Protocol Number:	MNK14344100
Document Description:	Final Statistical Analysis Plan
SAP Title:	A Multicenter, Randomized, Double Blind, Placebo Controlled Exploratory Study to Assess the Efficacy and Safety of Acthar® Gel in Subjects with Pulmonary Sarcoidosis
SAP Version Number:	3.0
Effective Date:	02FEB2022

Author(s):

For PPD: [REDACTED], [REDACTED] [REDACTED]
[REDACTED]
I approve this document
02 Feb 2022 11:21:10 -05:00
DocuSign

Approved by:

[REDACTED]
[REDACTED]
[REDACTED]
02-Feb-2022
Date (DD-MMM-YYYY)
Mallinckrodt ARD, LLC

[REDACTED]
[REDACTED]
Date (DD-MMM-YYYY)
Mallinckrodt ARD, LLC

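### SAP 9.5 tests six-visit questionnaire scores one visit at a time, on observed and LOCF values with no main analysis named, while the SAP's repeated-measures model serves only FVC and DLCO % predicted

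*SAP*

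**What the plan says.** For change and percentage change in the double-blind phase, SAP 9.5 states that "each outcome or questionnaire score will be evaluated using a two-sample T-test", with a Wilcoxon test as the option for non-normal data. On missing values it says "If result is missing at a post-baseline visit, the missing result will be imputed using the LOCF method", and then that "summaries and analyses will be conducted on both the observed values and the LOCF values". Neither run is called primary. WPAI is listed only and not tested.

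The questionnaires are given at every double-blind visit. Protocol 11.3 covers four ("The investigator or designee will complete the following procedures at Visit 3, 4, 6, and 7"), Protocol 11.4 adds Visit 5 to the same set ("the following will also be performed at Visit 5 by the investigator or designee"), and Protocol 11.5 covers Visit 8.

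In SAP 9.3 the treatment effect on DLCO and FVC % predicted is also "estimated using a mixed effect model with repeated measures (MMRM) model", with unstructured covariance and a fallback to AR1, then compound symmetry. The code in SAP 15.4 is generic ("model AnalVar = BASVAR TRT AVISITN TRT*AVISITN"), but SAP 9.5 does not call it.

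Protocol 15.5 makes LOCF the general rule for missing data and lists a mixed-effects model among possible additional analyses. Protocol 11.10 has subjects who stop early complete the Visit 8 procedures as soon as possible.

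**The concern.** LOCF treats a score from, say, Week 8 as though it were the Week 24 score. Prednisone tapering starts at Week 4 in both arms (Protocol 10.1), so there is no reason to expect scores to stay flat between an early exit and Week 24. Unequal dropout is plausible: the listed adverse reactions are corticosteroid-like (Protocol 6.4), and subjects whose events persist after a dose reduction are withdrawn (Protocol 8.1). In the cited chart review of 47 patients, "Eighteen patients (37%) discontinued drug within 6 months", 11 of them for toxicity.

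The observed-case run drops the same subjects at Week 24 and ignores their earlier visits. The method that uses partial follow-up is given to the endpoints with two double-blind visits and withheld from those with six. At stake is the reading of the patient-reported results: a spurious difference, a diluted real one, or two discordant answers with no rule for which to believe.

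**Working it through.** The plan states no sample size calculation, effect or SD for these scores, so there is no planned figure to reproduce.

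**1. Visits and tests.** Visits 3, 4, 6 and 7 (four), plus Visit 5, plus Visit 8, make six. PFTs in the double-blind phase after baseline fall at Visits 5 and 8 only (Protocol 7.2.2). SAP 9.5 names 18 tested scores: steroid toxicity 1, KSQ modules 5, KSQ overall scales 4, FAS 1, global assessments 2, MRC 1, LCQ 4. With two measures (change, percentage change) and two data sets, that is 18 × 6 × 2 × 2 = 432 between-arm tests. Week 24 has 18 × 2 × 2 = 72, or four per score.

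**2. LOCF bias with no true Week 24 difference.** Let c be the mean change from the last observed value to Week 24, the same in both arms, and dA and dP the dropout proportions. LOCF shifts each arm's Week 24 mean by −d × c, so the bias in the difference is −c × (dA − dP). All inputs are assumed. The 38% is 18/47 = 38.3% (the protocol prints 37%), the 23% is toxicity alone, 11/47 = 23.4%, and the 10% has no source. On a scale where higher is better:

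| Dropout | Early 6-point gain lost (c = −6) | Still improving (c = +6) |
|---|---|---|
| 38% v 10% | +6 × 0.28 = +1.68 | −1.68 |
| 23% v 10% | +6 × 0.13 = +0.78 | −0.78 |
| Equal | 0 | 0 |

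Against the 4-point meaningful change for KSQ and FAS (Protocol 7.2.6, 7.2.7), 1.68 is 42% and 0.78 is about 20%. Simulating the lost-gain case (28 v 27 subjects, SD 12, within-subject correlation 0.6, dropout unrelated to score) gave a bias of 1.6 to 1.7 points and about 8% false positives at 38% v 10%, and about 5.6% false positives at 23% v 10%. In the 38% v 10% case the observed-case test had bias of about 0 and 5% false positives.

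**3. Dilution of a real benefit.** Take a linear course over six visits, with dropouts' last visit spread evenly over the first five. They have reached on average (1+2+3+4+5)/(5 × 6) = 0.5 of the Week 24 change. A true benefit of 1 unit (active 1, placebo 0) becomes 1 − 0.5 × dA: 0.95, 0.90 and 0.81 at 10%, 20% and 38%. The placebo rate does not enter, so equal dropout does not prevent this.

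**4. Dropout related to the score.** Simulation of 1,000 trials per row (27 v 28 subjects, SD 1, correlation 0.9 per visit lag, dropout more likely after a worse last score). Entries are the mean Week 24 difference in SD units and the rejection rate at two-sided 0.05.

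| Scenario (nominal dropout) | LOCF | Observed | MMRM |
|---|---|---|---|
| No difference, both arms improve 1 SD, 38% v 10% | −0.17, 8.6% | +0.10, 5.4% | 0.00, 5.9% |
| No difference, both arms decline 1 SD, 38% v 10% | +0.15, 8.1% | +0.15, 6.1% | 0.00, 4.3% |
| No difference, both arms improve 1 SD, 20% v 20% | 0.00, 5.7% | 0.00, 6.1% | 0.00, 6.2% |
| True benefit 0.8 SD, 38% v 10% | 0.60, 54% | 0.88, 78% | 0.78, 72% |
| True benefit 0.8 SD, 20% v 20% | 0.72, 73% | 0.78, 73% | 0.79, 78% |

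Realised dropout differed from nominal (33% v 9% in the first row, 47% v 14% in the second). In the fourth row the observed-case power partly reflects an overestimated effect. The data were generated as missing at random, the assumption under which MMRM is valid.

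**The case against.** - **LOCF is one of two runs.** This stands. The observed-case result will be reported beside it, and under dropout unrelated to score that result is unbiased. Step 4 shows that this protection fails when dropout depends on the score and differs by arm, although the observed-case false-positive rate stays near nominal (5.4% to 6.1%).
- **The inputs are borrowed.** This stands. The chart review was retrospective and uncontrolled, in advanced disease; 4 of its 18 stoppers left over cost; and this trial allows a dose reduction before withdrawal. The size is therefore a range, not a forecast.
- **LOCF and t-tests are the protocol's own plan, in an exploratory study.** True; the SAP does not depart from the protocol here. But Protocol 15.5 also allows mixed-effects models and further imputation, and the tests still use two-sided 0.05.
- **MMRM has its own weaknesses.** It assumes missing at random and projects from those who stayed. Unstructured covariance over six visits needs 6 × 7/2 = 21 parameters from 55 subjects, and the SAP 15.4 code sets no small-sample degrees of freedom. I find no SAP rule placing early-termination assessments in a visit window. If they are stored as Visit 8, an early value would count as Week 24 in the observed-case run and in an MMRM too. The fix must cover these points.

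**Conclusion.** The point holds as an improvement to make, not as an error that invalidates the plan. The SAP leaves four Week 24 comparisons per questionnaire score without saying which counts, and it uses the weaker methods where the repeated-measures model has most to offer. The LOCF bias is about 1.6 to 1.7 points at 38% v 10% dropout and 0.8 at 23% v 10%, for an assumed 6-point change after dropout. It is nil under equal dropout with no true difference, but a true benefit is diluted even then.

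A reader might infer three stronger things that the documents do not support:

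- That dropouts' early values are the plan's Week 24 results. By the stated LOCF rule this happens only in the LOCF run.
- That the bias favours Acthar. It favours the arm with more dropout if an early gain is lost and goes against that arm if scores are still improving. The documents fix neither the course nor which arm loses more subjects.
- That 38% is this trial's expected dropout. No rate is planned for either arm.

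**What to change.** In SAP 9.5, name as the main comparison for the KSQ, FAS, LCQ and steroid toxicity scores an MMRM on change from baseline over Visits 3 to 8. Include baseline score, treatment, visit and treatment-by-visit; use unstructured covariance with the SAP 9.3 fallback order and small-sample degrees of freedom such as Kenward-Roger. Report the Week 24 LS mean difference with 95% CI. Keep the planned rank-based option for the five-grade MRC scale, and say which method applies to the two global assessments.

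Also:

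- Assign early-termination assessments to the visit window in which they occurred, not to Visit 8.
- Add the baseline covariate to the SAP 9.3 text, which omits it, so that it matches the SAP 15.4 code.
- State the missing-at-random assumption, and keep the observed-case and LOCF tests as sensitivity analyses.
- Declare the change in SAP 13.

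The cost is SAP wording, a windowing rule and reuse of existing code; no new data are needed. The downside is that, with about 55 subjects and six visits, the covariance fallback may be needed.
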